For external partners, any request of access to data will be assessed and will follow the ethic and regulatory procedures of India.

Quality Assurance and Quality Control Protocols

X.

- All staff within project site have received comprehensive training on the care and management of HCV infection.
- All staff directly involved in the recruitment, consenting, data collection and data management for this study will receive comprehensive training in the conduct of research in full compliance with the Declaration of Helsinki (21) and International Ethical Guidelines for Biomedical Research Involving Human Subjects (22).
- The quality of data collection and management will be routinely monitored by the onsite data manager and cross-checked by the MSF epidemiologist based in Delhi.
- Data management, monitoring, quality control, data sharing and data analysis in the Manipur sites will be in accordance with ethical standards of confidentiality and anonymity. Data will be collected, stored, cleaned and analyzed by study staff. Participant names will not be entered in the database. Data will be stored securely and password protected, with de-identified data made available to NACO on request. Regular reporting of study progress and patient outcomes will be provided to NACO at an agreed interval.
- In addition to the performance of internal and external quality control procedures set up by each laboratory and to ensure quality control of the different HCV tests, a proficiency testing will be proposed to the laboratories using characterized samples. This procedure will be repeated on a regular basis, and will include panels of samples with different viral concentration and different genotypes.

XI. Ethical considerations & respondent protection measures

This protocol, recruitment materials, informed consent forms and questionnaires, contained in Annexes have been submitted for ethical review to the MSF Ethical Review Board and received ethical clearance. The protocol has also received ethical clearance from Regional Institute of Medical Sciences, Lamphelpat, Imphal, India on 23rd March 2016. This study has been approved by National Aids Control Organization, New Delhi (nodal body of Ministry of health, Govt. of India) on 3rd Nov 2016

a). Risks to participants

Study participation is not expected to convey any major risks to patients. The specific procedures of the study only concern data collection and their coded use. The interview to assess treatment adherence and to identify potential risk factors associated with treatment failure are conducted as part of the patient clinical management, the researches will access the coded data of those consenting to be part of the study. There is no additional data to be collected that is already not part of the clinical management of these patients.

Similar to blood taking during routine clinical care, blood taking for the current care or for storage may cause a slight discomfort.

b). Direct Benefits for participants

HCV care and treatment are not yet available in the MoH structures. Each study participant will benefit from diagnosis and treatment for the HCV infection. Participants will receive direct feedback on the success of their current treatment.

c). Indirect Benefits for participants

The study results are expected to support optimization of HCV patient management, co-infected by HIV and inform optimization of treatment regimens, in limited resource settings. Participants will indirectly benefit from the expected effects of the study findings on future HCV care and follow-up.

d). Protection from risk

There will be no electronic link between the Identification number and the name of the patient as names will not be entered in the database.

e). Consent form

Consent form has been approved by the MSF Ethics review Board (ERB) and will be translated into the 5 main local languages in Manipur State, as deemed possible.

A trained clinician/counselor will administer the information sheet verbally, encouraging questions. When it is deemed the subject has a good understanding they will be asked to sign the consent form. The subject will sign the informed consent document prior to any study-related analysis of their data. Subjects will be given the opportunity to discuss the study with their surrogates or think about it prior to agreeing to participate. The participant, if functionally illiterate, may sign the consent by marking with a thumbprint on the signature line. The presence of a witness who will also have to sign the document will also be encouraged. The subject may withdraw consent at any time throughout the course of the study. A copy of the signed informed consent document will be given to subjects for their records. The rights and welfare of the subjects will be protected by emphasizing to them that the quality of their clinical care will not be adversely affected if they decline to participate in this study.

XII. Timelines

The study has an estimated start date of December 2016, and with the end of inclusions being December 2018. Table 2 provides a breakdown of the study timetable for the Manipur sites.

Table 4: Study Timeframe

Activities	Time
Protocol development and submission to MSF Ethical Committee	Jan 2016-April 2017-
National Protocol developments and submission to NACO	April 2016 – Nov 2016
Field preparation and pilot study	Nov-Dec 2016
Recruitment	May 2017 to May 2019
Follow-up patients	May2017 toAug 2019
Field data management	May 2017 to Aug 2019
Regular Data analysis and Monitoring_ interim reports	May 2016 to Aug 2019
Final report (including outcomes)	Dec 2019
External communication	Jan 2020

7. FACILITIES IN TERMS OF EQUIPMENT, ECT, AVAILABLE AT THE INSTITUTION / ORGANISATION FOR THE PROPOSED INVESTIGATION

The treatment activities on which this observational study will be performed are on-going programmatic activities within the MSF clinics located in Churachandpur, Chakpikarong and Moreh. Within these locations MSF in partnership with NACO, operate as outpatient facility with associated on-site laboratory capacity. Each of these laboratories is capable of performing routine biochemistry, haematology, CD4 counts, serological testing HIV / HCV / HBV / Syphilis and Microscopy. Each also has a GeneXpert machine. In addition a mobile Fibroscan machine is present and can be moved between these sites.

Each clinic is computerised with password protected access to currently used data collection tools

No additional equipment will be required to conduct the observational cohort study

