2. PROJECT SITES

- a. Doctors without Borders Clinic, [name].
- b. Doctors without Borders Clinic [name]
- c. Doctors without Borders Clinic, [name]

3. BACKGROUND & RATIONALE FOR THE STUDY AND ITS APPLICATION WITH RESPECT TO THE PROGRAMME PRIORITIES UNDER NACP-IV.

INTRODUCTION

Médecins Sans Frontières (MSF) has been active in Manipur state since 2004. MSF has ART centres in Churachandpur, Moreh and Chakpikarong providing care and treatment to over 1600 people living with HIV/AIDS (PLWHA). MSF has a Public Private Partnership (PPP) with the National AIDS Control Organisation (NACO). Both parties signed an MOU in which it was agreed to set up a collaborative ART project between NACO and MSF that would seek to be a model for high quality provision of ART and associated healthcare and medical management of PLWHAs in its sites in India. As part of this commitment to care, MSF commenced hepatitis C (HCV) treatment for HIV co-infected individuals in July 2015 in Churachandpur.

The rapidly evolving HCV landscape, including new DAA based regimens, provides novel treatment options and opportunities to treat patients successfully, with fewer side effects and simplified surveillance in low resource settings. The aim of this study is to assess the effectiveness and safety of chronic HCV treatment amongst HIV positive co-infected patients

receiving treatment in accordance with current WHO and other International treatment protocols and guidelines, within real world settings.

A prospective longitudinal cohort study was chosen to support the monitoring of the introduction of these new regimens and contribute to post licensure surveillance. An important caveat to note is that this study is in no way a Phase four clinical trial or a pharmaco-vigilance study. The methodology described is in accordance with an observational study of a cohort of patients under HCV treatment in the MSF ART centres and analysis of routinely collected clinical data.

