6. DETAILED RESEARCH PLAN

METHODOLOGY

I. Study Design

The study will be a prospective longitudinal cohort study, which will monitor the diagnosis, treatment and follow-up of the HIV patients identified with a chronic hepatitis C within 3 clinic sites in Manipur; Churachandpur, Chakpikarong and Moreh.

The analysis of routinely collected clinical data will facilitate the assessment of the effectiveness of HCV treatment among patients with chronic hepatitis C, co-infected with HIV, from time of confirmation of their HCV Viral load until SVR12, death, lost to follow up, medical decision to exit the study or transfer out, whichever comes first.

The study will assess implementation of new recommended HCV-curative regimens in real world settings, not specific new drugs. The specific treatment regimens used, including new DAAs, will be selected in accordance with current WHO, international and national recommendations and protocols (18-20). Of the new DAA's, only drugs registered and available in India will be used in accordance with international and national recommendations and protocols.

II. Study population

The study population will include HIV infected patients from Manipur state diagnosed with chronic hepatitis C (viral load HCV positive) meeting eligibility criteria. These patients will be directly identified in the MSF sites.

III. Sample size

The sample will exhaustively include all patients meeting the inclusion criteria in each site for a period of two years. Currently MSF, in collaboration with NACO has approximately 1600 adult patients being actively followed up for HIV care within Manipur. The overall rate of HIV-HCV co-infection, based on HCV serological screening performed to date is approximately 27%. Assuming 80% of serologically positive patients have chronic hepatitis C, the minimum sample size expected for this study will be 345 patients.

IV. Sampling design

The sample will exhaustively include all patients meeting the inclusion criteria in each site for a period of two years.

Inclusion and Exclusion criteria:

When the results of VL tests become available, all patients over 18 years will be invited to participate in the study, if they fulfill eligibility criteria. Inclusion is not linked with eligibility for HCV or HIV *treatment*. A criterion of non-eligibility to treatment is not considered as inclusion or exclusion criteria for study participation¹.

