The individual may withdraw consent at any point during the study with no impact on treatment and care.

¹ Eligibility for study inclusion and HCV treatment are different. The study will also include HCV positive patients who do not receive treatment either due to non-priority of treatment or presence of clinical contraindications. (These patients may receive treatment at a later date). This is intended to fulfil secondary objectives 'i' and 'j'. However patients will receive standard HCV treatment and care in the event of non-eligibility to the study or refusal to participation in the study.

Table 1: Study participant eligibility criteria

	Eligibility criteria for study inclusion	Eligibility criteria for HCV treatment
Inclusion criteria	
 • HIV/HCV co infection independent of the stage of liver disease • Over 18 years of age • HCV viral load greater than 12UI/mL • HIV positive status confirmed by the national and MSF algorithm • Able and willing to provide informed consent • Willing to comply with all study procedures 	Clinical Review 
 • Confirmed HCV infection • HIV infection controlled on ART or asymptomatic HIV infection with CD4 count >500/ μL in the absence of ART • Controlled drug use • Controlled opportunistic infections • Hemoglobin threshold: 9 g/dL
		Psychosocial Review 
 • Adherent to HIV treatment and appointments • Controlled use of substances (if relevant) • No evidence of uncontrolled psychiatric disorder
Exclusion criteria	
 • Individual aged less than 18 years • Individual does not consent to be part of the study. 	Clinical Review 
 • Evidence of hepatocarcinoma • Advanced/terminal heart or pulmonary or renal or other disease • Active, uncontrolled opportunistic Infections • First 3 months of a new ART regimen (unless minor ARV change for toxicity); • Pregnancy or planning pregnancy in following months, unwillingness to use contraception Breastfeeding women.
		Psychosocial Review 
 • Unwillingness of the patient to adhere to HCV treatment & ART • Uncontrolled severe psychiatric disorder. • Unstable substance use

V. Statistical methods to be used

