Question 21 on CRF1 (Appendix 2) will identify patients who have consented to be part of the cohort study.

21_Did the patient sign an informed consent for the cohort study Yes No DK

In the event of a serious adverse event occurring, the Indian national "Suspected Adverse Drug Reaction Reporting Form" will be completed. This can be found at the following web link:

<http://www.ipc.gov.in/PvPI/ADRReportingForm.pdf>

VII. Implementation / Operational Plan

As outlined within the introduction, MSF has been active in Manipur since 2004 and now has ART centres in Churachandpur, Chakpikarong and Moreh providing care and treatment for over 1600 patients living with HIV/AIDS (PLWHA). As part of MSF's commitment to provide high quality care to PLWHA, treatment of HCV for HIV co-infected individuals was commenced in 2015. As such, the treatment activities, on which this prospective observational study will be based, are a part of MSF's on-going routine operational activities.

The following describes these current operational activities in addition to supplementary activities which will be incorporated for the conduct of a scientifically rigorous prospective observational study.

Participant's recruitment

Serological screening for HCV has been routinely undertaken on all confirmed HIV positive patients entering within the MSF facility since 2012. Serological rapid tests, approved by Indian regulatory authorities have been used for this purpose. During 2015 confirmation of active HCV infection was commenced within the program with Real time PCR for virology on a Roche platform within Babina private laboratory, Imphal.

Patients with a HCV viral load detectable and a co-infection with HIV will be proposed to join the study, if they fulfil eligibility criteria for the study. Patients eligible to participate in the study will receive comprehensive information about the treatment regimen and the study, its risks and benefits, the study's objectives and procedures.

In addition to the verbal information, a Patient Information Sheet concerning the study will be provided, with contact information (Appendix 5).

For individuals who are eligible and interested in participating, the health staff will obtain informed consent from the individual to participate to the study (Appendix 5) Consent form and Patient Information Sheets will be translated and back translated in the local languages most adapted to the patients, where possible.

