The following definitions will be considered:

In case of viral load detectable 12 weeks after end of treatment, the outcome will be considered as treatment failure.

- Deaths will be recorded by the medical teams, notified by a close relative or friend or reported by a tracing team (for programs implementing such strategy).
- Loss to follow-up is defined as two months after a planned date of appointment without contact, among patients who were not dead or transferred out.
- Transfer out is defined as a patient who has been transferred to another medical facility or consultation and for whom the treatment outcome is not known, without the possibility to continue the HCV follow up in the study site. Patients that require to be transferred out will be informed that it is very unlikely that they can continue HCV treatment. In case of possible return to the study site, the patient may be proposed again to enter in the study and informed consent will be sought again. The same identification number will be used.
- Exit due to medical reason is defined as a cessation of follow decided by the clinicians, in collaboration with the patients, due to other more urgent medical needs.

Secondary endpoints:

- Proportion of patients included in the cohort by socio-demographic characteristics: age group, sex, occupation, marital status, risk factors of HCV exposition

- Proportion of patients included in the cohort by clinical and biological characteristics: genotype, HCV viral load, liver fibrosis staging, presence of ascites, HIV WHO staging at baseline, CD4 count and HIV viral load prior to HCV treatment, HBV status, Child pugh score, hematology, biochemistry
- Proportion of patients with HBV infection defined as a positive RDT with HBV AgS diagnosis
- Distribution of liver fibrosis stage among included population
- Proportion of patients with HCV treatment initiated
- Proportion of SVR 12 among the patients having completed HCV treatment.
- Proportion of patients with SVR 12 stratified by regimen and by genotype
- Proportion of patients with SVR 12 stratified by site
- Mortality among the patients in the HCV cohort overall, and among patients who initiated treatment or among patients without treatment initiation
- Proportion of defaulters during before, during and after treatment
- Proportion of patients transferred out, and for whom medical decision to interrupt HCV follow up has been taken

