- Frequency and type of demographic, clinical and biological risk factors associated with treatment outcomes: age , sex, liver fibrosis stage, child pugh score, genotype, clinical symptoms, comorbidities with HBV infection , addiction
- Concerning the safety of HCV treatment: Frequency and type of treatment-related side effects or events that cause modification of dosage of the HCV treatment
- Frequency and type of treatment-related side effects that cause permanent interruption (discontinuation) of the HCV treatment
- Concerning the feasibility of HCV treatment: Proportion of patients included in the cohort but non eligible to treatment at the first assessment, by clinical and biological characteristics, over time (yearly eligibility assessment): HCV viral load, liver fibrosis stage, child pugh score, presence of ascites,HIV viral load
- Frequency and type of demographic, clinical and biological risk factors associated with non-eligibility to treatment: age , sex, fibrosis stage, child pugh score, genotype, clinical symptoms, biological anomalies, comorbidities with HBV infection, addiction
- Frequency of reporting of missed doses by patients

IX. Data management

Data Collection Tools

Paper based questionnaires and lab forms will be used for collection of individual baseline information, clinical evaluation information, laboratory results and treatment information. The different CRFs are presented in Appendix 1 and 2. Other data collection tools may be used in the laboratory. Questionnaires will be pre-tested prior to initiation of data collection. Study forms will be linked through unique study numbers assigned to study participants. Personal identifier information will be recorded on separate forms, and will be kept separately to maintain confidentiality.

Listing of data collection questionnaire (Appendix 1 & 2):

- Baseline information
- Consultation form
- Comorbidities form
- Biological form

- Adverse Events form

In case of adverse events, specific reports will be filled, initial and follow up reports (Appendix 3).

Prior to the inclusion in this cohort, the patient may be under medical follow up for his HIV and / or HCV care. These data are collected on different tools. Some information would be used for this study. As example, the CD4 count at enrolment will be found in the HIV database used in the HIV care facility. The source of the data is specific to each site. The data will be reported to the HCV database.

Data Management and Monitoring

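### Observation starts at viral-load confirmation but entry is by later consent, so for patients confirmed before recruitment any mortality or pre-treatment default figure dated from confirmation is too low

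*Protocol*

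**What the plan says.** Section 6.I (Study Design) sets the observation window "from time of confirmation of their HCV Viral load until SVR12, death, lost to follow up, medical decision to exit the study or transfer out". Observation ends at the earliest of these.

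Three other places bear on when patients can enter:

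- Section 6.VII (Participant's recruitment): "During 2015 confirmation of active HCV infection was commenced within the program with Real time PCR". The introduction in section 3 adds that "MSF commenced hepatitis C (HCV) treatment for HIV co-infected individuals in July 2015 in Churachandpur".
- Table 1 lists as an exclusion: "Individual does not consent to be part of the study". It sets no limit on the age of the qualifying viral-load result.
- Section 6.XII gives a study start of December 2016 in the text, but Table 4 gives recruitment as "May 2017 to May 2019".

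Section 6.IX recognises earlier care: "Prior to the inclusion in this cohort, the patient may be under medical follow up for his HIV and / or HCV care". The secondary endpoints in section 6.VIII include "Mortality among the patients in the HCV cohort overall", the same split by whether treatment was started, and the proportion defaulting before, during and after treatment.

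**The concern.** The time origin and the entry condition do not match. To be in the cohort, a patient confirmed in 2015 or 2016 must still be alive and in contact when recruitment opens. Patients who died in between, or left and did not return, never consent and appear in neither numerator nor denominator. Those who do consent bring with them a stretch of time that is free of death by construction. This is left truncation, and counting that stretch as time at risk creates immortal time.

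The endpoints exposed are mortality and pre-treatment default. Untreated and waiting patients matter most, because the cohort was widened to describe them (objectives i and j) and they can carry the longest gap between confirmation and consent. The distortion may therefore differ between the treated and untreated groups whose mortality is to be shown side by side.

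**Working it through.** **The plan's own figure.** Section 6.III: 1600 patients in care × 0.27 seropositive × 0.80 chronic = 345.6, against a stated 345. It reproduces. It also shows that the expected sample comes from the existing clinic pool, so patients confirmed before recruitment are plausibly a real part of it.

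**Length of the gap for a patient confirmed during 2015.**

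- Recruitment from December 2016: 12 months (confirmed December 2015) to 23 months (January 2015).
- Recruitment from May 2017: 17 to 28 months.

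Patients confirmed in 2016 have shorter gaps. Patients confirmed during recruitment have almost none, because section 6.IV invites them when the result arrives.

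**Effect on a rate.** Let *s* be the share confirmed before recruitment, *L* their mean gap to consent and *F* the mean follow-up after consent. With a constant hazard and events countable only after consent,

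reported rate / true rate = F / (F + s × L).

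The protocol gives none of *s*, *L* or *F* as means, so these are assumptions: *s* 25-75%, *L* 6-11 months, *F* 9-18 months.

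- Least favourable: 9 / (9 + 0.75 × 11) = 9 / 17.25 = 0.52.
- Most favourable: 18 / (18 + 0.25 × 6) = 18 / 19.5 = 0.92.
- Middle (50%, 8.5 months, 12 months): 12 / (12 + 0.5 × 8.5) = 12 / 16.25 = 0.74.

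If the earlier group had all been confirmed in 2015, with gaps of 12 to 28 months, a 50% share and 12 months of follow-up would give 12 / (12 + 6) = 0.67 down to 12 / (12 + 14) = 0.46.

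**Effect on a proportion, and check of the remedy.** A simulation used an assumed mortality of 3.0 per 100 person-years and, as an extreme case, a gap spread evenly over 0-28 months for every patient.

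| Follow-up after consent | Rate counted from confirmation | Rate counted from consent | Died, among enrolled | Died by the same date, among all confirmed |
|---|---|---|---|---|
| 12 months | 1.4 | 3.0 | 3.0% | 6.3% |
| 27 months (Table 4 maximum, May 2017 to August 2019) | 2.0 | 3.0 | 6.5% | 9.7% |

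In both rows 3.4% of confirmed patients die before they could consent. Entry at consent recovers the assumed rate. The proportion among enrolled patients is sound as a statement about the period after inclusion, and too low if described as running from confirmation.

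**The case against.** The strongest reply is that the protocol plans no person-time analysis. Section 6.V names summary statistics, two-group tests, unspecified regression models and diagnostic accuracy measures, but no incidence rate or survival curve. Default is stated as a proportion and mortality has no stated scale. The sentence in section 6.I speaks of assessing treatment effectiveness and does not expressly define time at risk for death or default. Details of the time scale could also be settled in an SAP. For a plain proportion, moving the origin does not change who was enrolled and recovers no missed death.

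Most of this stands, and it limits the point to figures presented as running from confirmation. It does not remove it. Section 6.I is the only window the protocol states, and an analysis plan that followed it would inherit the mismatch. For proportions, the remedy is to describe the figure as events after inclusion, which needs no recovery of missed deaths.

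Three stronger readings are tempting, and the documents do not support them:

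- A reader might infer that no event at all can occur before consent. That holds for death. Under section 6.VIII a patient can meet the loss-to-follow-up definition (two months without contact after a planned appointment), return, and then consent.
- A reader might infer that the primary result is biased in this way. SVR12 is a proportion among patients who started treatment, and this person-time does not enter it.
- A reader might take the ratios above as the bias in a planned result. They apply to a rate the protocol does not commit to, with an earlier-confirmed share it does not give.

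**Conclusion.** The point holds for secondary endpoints. The stated origin precedes the earliest possible entry for anyone confirmed before recruitment, and nothing in the protocol starts time at risk at consent or provides for delayed entry. Mortality or pre-treatment default presented from viral-load confirmation would be understated, by dilution if a rate or curve and by selection if a proportion.

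The direction is clear; the size is not known. The 0.52-0.92 range for a rate rests on the assumed share, gap and follow-up and on a constant hazard. It approaches 1 as the earlier-confirmed share falls. The change is worth making before analysis, but it does not threaten the primary endpoint.

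**What to change.** - In section 6.I, state that time at risk for mortality, default and any other time-based endpoint starts at the date of consent (inclusion). Alternatively, keep viral-load confirmation as the time scale with delayed entry at consent.
- In section 6.VIII, word the mortality and default proportions as events after inclusion.
- Report the gap from confirmation to consent as a baseline descriptor, with the share of participants confirmed before recruitment opened.
- Record the consent date in the database. The item shown in section 6.VI (question 21 of CRF1) is only Yes/No/DK. The CRF1 interview date is not a safe substitute, because section 6.VI says the forms were already in clinical use and that date may precede consent. The viral-load date is already on the laboratory form.
- Reconcile the two recruitment periods in section 6.XII.

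The cost is a few sentences, one date field and an entry date in any survival set-up. The downside is a shorter stated follow-up and less favourable mortality and default figures.

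### Observation ends at SVR12, which only treated patients can reach, and no end is named for untreated patients, so crude mortality by treatment initiation would rest on unequal windows

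*Protocol*

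**What the plan says.** Section 6.I gives one observation window for the whole cohort. It opens "from time of confirmation of their HCV Viral load" and runs "until SVR12, death, lost to follow up, medical decision to exit the study or transfer out, whichever comes first". Section 6.VIII places the SVR12 measurement 12 weeks after the end of treatment, and Tables 2 and 3 give regimens of 12 or 24 weeks.

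Untreated patients are enrolled on purpose. Footnote 1 to section 6.IV says: "The study will also include HCV positive patients who do not receive treatment either due to non-priority of treatment or presence of clinical contraindications". It adds: "These patients may receive treatment at a later date". Objective j in section 4 is to describe how non-eligible patients evolve, and a feasibility endpoint in section 6.VIII follows non-eligibility "over time (yearly eligibility assessment").

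The mortality endpoint in section 6.VIII reads: "Mortality among the patients in the HCV cohort overall, and among patients who initiated treatment or among patients without treatment initiation". It does not say whether this is a proportion or a rate. Table 4 in section 6.XII gives the follow-up period as "May2017 toAug 2019", with recruitment from May 2017 to May 2019. The sentence above that table instead puts the start at December 2016 and the end of inclusions at December 2018.

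**The concern.** One of the listed end events, SVR12, is open to treated patients only. A treated patient who stays in care leaves the window 24 or 36 weeks after starting treatment. An untreated patient who stays in care meets no listed end event. The yearly reassessment and objective j imply that such a patient continues until follow-up closes.

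Deaths would then be counted over a shorter period in one group than in the other, and the two figures are listed next to each other. With crude proportions, the treated figure comes out lower even if treatment has no effect on survival. Deaths after SVR12, including any from later liver disease, also fall outside the stated window, so they are missing from both the treated and the overall figure. No later choice of summary measure can recover deaths that were not recorded.

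**Working it through.** The protocol gives no follow-up length per group, no death rate and no waiting time to treatment, so there is no figure of its own on this point to reproduce. Its only related figure, the cohort size, does reproduce: 1600 × 0.27 × 0.80 = 345.6, stated as 345.

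**Inputs from the protocol.** Recruitment lasts 24 months and close is at month 27 (Table 4). Regimens last 12 or 24 weeks, and SVR12 is 12 weeks after the end of treatment.

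**Assumptions.** Accrual is uniform, nobody exits early, untreated patients are followed to close, the wait from inclusion to treatment is 0 or 13 weeks, and both groups have the same death rate of 3 per 100 person-years.

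**Untreated window.** Mean = 27 − 24/2 = 15 months, or 15 × 52.18/12 = 65.2 weeks. The range is 3 to 27 months, or 13.04 to 117.40 weeks, a width of 104.36 weeks.

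**Treated window.** Let T = wait + regimen + 12 weeks, cut at close for late inclusions. Mean = T − (T − 13.04)²/(2 × 104.36).

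| Wait (weeks) | Regimen (weeks) | T | Mean observed (weeks) | Shortfall against 65.2 |
|---|---|---|---|---|
| 0 | 12 | 24 | 24 − 0.58 = 23.4 | 64% |
| 0 | 24 | 36 | 36 − 2.52 = 33.5 | 49% |
| 13 | 12 | 37 | 37 − 2.75 = 34.25 | 47% |
| 13 | 24 | 49 | 49 − 6.19 = 42.8 | 34% |

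**Crude proportion dying.** This is the mean of 1 − exp(−0.03 × years observed). Untreated: 3.67%. Treated, in table order: 1.34%, 1.91%, 1.95% and 2.43%. The ratios are 2.74, 1.92, 1.88 and 1.51. At 1 or 6 per 100 person-years they are nearly the same (1.5 to 2.8).

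**Sensitivity to the wait.** At 26 weeks, among patients included early enough to start before close, the treated means are 46.8 and 54.9 weeks and the ratios about 1.4 and 1.2. At 12 months the treated window before cut-off is 17.5 to 20.3 months, longer than the untreated 15, so the window effect alone reverses.

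**Sensitivity to the dates.** With inclusions from December 2016 to December 2018 and close in August 2019, the untreated mean is 32 − 12 = 20 months (87 weeks). The ratio is about 1.8 to 3.5 at a 0 to 13 week wait and 1.5 to 1.8 at 26 weeks.

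**A second effect in the same direction.** The ratios above count time waiting as time at risk in the treated group. In practice a patient who dies while waiting is never treated, so the treated group carries immortal time. A simulation at a common rate of 2 per 100 person-years (70% treatable and an exponential wait, both assumed) shows two things:

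- With long waits, crude mortality stays about three times higher in the untreated (3.1% to 3.3% against 0.95% to 1.0%).
- A person-year rate by ever/never-treated status does not cure this: at a mean wait of 2 months it gives 2.56 untreated against 1.53 treated. Counting time before initiation as untreated gives 1.99 to 2.01 against 2.00 to 2.03.

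**The case against.** The strongest reply has four parts.

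- **No comparison is planned.** None of the objectives contrasts treated with untreated mortality, and untreated patients are there for two descriptive objectives. The groups also differ by design, since hepatocarcinoma, terminal disease and uncontrolled infection bar treatment. This stands. A reader might infer that the protocol plans to claim a survival benefit; it does not. Even equal windows would not make the two figures a treatment contrast.
- **The measure is open.** The endpoint says mortality, not proportion, and an analysis plan may specify a time-updated rate. This also stands, so the spurious ratio is conditional. The observation rule is not open, however: it is written in section 6.I, and a rate cannot restore deaths it leaves out.
- **The end for untreated patients is inferred.** A reader might take follow-up to study close as a stated rule. It is not stated; it follows from the yearly reassessment, objective j and Table 4. What the text does show is that no end is named for them.
- **The window sentence concerns effectiveness.** It does not say that deaths go unrecorded after SVR12, and CRF2 item 290 lists cure, but not virological failure, among the reasons for ending follow-up. So a reader should not conclude that every death after a failed SVR12 is certainly lost. Still, this is the only window the protocol gives, and the schedule in Appendix 3 (Table 3.0) stops 12 weeks after treatment.

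The scale is also modest. With the risks above and an assumed even split of 345 patients, expected deaths are about 6 untreated (172.5 × 3.67%) and 2 to 4 treated (172.5 × 1.34% to 2.43%).

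**Conclusion.** The concern holds in a conditional form. The stated window ends at an event that only treated patients can reach, no end is named for the others, and mortality is listed by treatment initiation. If it is reported as crude proportions, or by ever/never-treated status, untreated mortality will look higher at the same death rate.

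On Table 4 dates with a wait of 0 to 13 weeks, the crude ratio produced by the windows alone is about 1.5 to 2.7. It rests on uniform accrual, no early exits, untreated follow-up to August 2019, and a wait that the protocol does not give. Longer waits shrink the window effect and can reverse it, while immortal time then works against the untreated figure. The earlier inclusion dates enlarge the window effect.

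The endpoint is secondary and descriptive. The primary SVR12 endpoint is not affected.

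**What to change.** For the mortality endpoint only:

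1. In sections 6.I and 6.VIII, state one administrative close date for vital status that applies to all participants, treated or not, and say that it does not stop at SVR12. Reconcile the two sets of inclusion dates in section 6.XII, because the length of follow-up depends on them.
2. Take the date of death or last contact from HIV clinic records where available. Section 6.IX already draws on the HIV database ("The data will be reported to the HCV database"), but that text concerns information from before inclusion and says the source differs by site. Check first that consent and each site's data source cover use after SVR12.
3. Report deaths per 100 person-years with treatment as time-varying, so that time before initiation counts as untreated. A common close date alone would leave the immortal time in place.
4. Present the figures as descriptive, because the groups differ by eligibility for treatment.

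The cost is a few sentences and modest data linkage at close, which may differ by site. No visits or tests are added, and the SVR12 analysis is unchanged.
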